7.2.2. Independent variables

Socioeconomic position (SEP) will be derived from highest educational qualification, coded as lower (1 = No formal qualifications; 2 = 1–3 GCSEs; 3 = 4+ GCSEs; 4 = A level) or higher (5 = Certificate of higher education (CertHE); 6 = Diploma of higher education (DipHE); 7 = Bachelor; 8 = Master’s degree; 9 = Doctorate).

Impulsivity. Items from the Barratt Impulsiveness Scale will be coded from 1 to 4. The higher the summed score for all items, the higher the level of impulsiveness (min. = 30, max. = 120). McDonald’s Omega will be calculated as an indicator of internal consistency.

Inhibition. For correct responses, the median reaction times (RTs) in incongruent and congruent trials will be calculated [53,54]. The difference in median RTs between incongruent vs congruent trials will be calculated [incongruent RT – congruent RT] = *The Stroop interference effect*. Higher scores indicate poorer response inhibition.

Portion size appropriateness. For each participant the average selected portion size will be calculated in kcal.

Satiety responsiveness. Items will be coded from 1: *strongly disagree*, to 5: *strongly agree* and their mean will be calculated. A higher score indicates a higher satiety responsiveness. McDonald’s Omega will be calculated as an indicator of internal consistency.

Plate clearing tendencies. Response options range from 1 to 5: 1 = strongly disagree, to 5 = strongly agree. Responses will be averaged. Higher scores indicate higher plate clearing tendencies. McDonald’s Omega will be calculated as an indicator of internal consistency.

Perceived food insecurity. Based on the recommendations of the authors of the questionnaire [55] responses to the 6 questions about food insecurity will be coded as affirmatives (i.e. “yes”, “often true”, “sometimes true”, “almost every month”, “some months but not every month”) and negatives (i.e. “no”, “never true”, “only 1 or 2 months”). Coding of food security is based on the number of affirmatives as follows: 0-1 = “food secure”, 2-4 = “food insecure without hunger”, 5-6 = “food insecure with hunger”. The responses “don’t know” and blank responses reflect missing data, which will be imputed following best practice guidance [55].

Resource availability in childhood. Each item will be coded from 1 = strongly disagree, to 7 = strongly agree and an index of resource availability in childhood will be calculated as the mean of the three items. McDonald’s Omega will be calculated as an indicator of internal consistency.

Food choice motives. Both health and weight control scores will be computed by averaging ratings for individual items of each dimension (health motivation: 6 items; weight control motivation: 3 items). Response options range from 1 to 4: 1 = Not at all important; 2 = A little important; 3 = Moderately important; 4 = Very important. Higher scores indicate stronger motives around health and weight control respectively. McDonald’s Omega will be calculated as an indicator of internal consistency for both scores.

Compensatory health beliefs. Response options range from 1 to 5: 1 = not at all, 2 = a little, 3 = somewhat, 4 = quite a bit, 5 = very much. Higher scores indicate stronger compensatory health beliefs. McDonald's Omega will be calculated as an indicator of internal consistency and if this is consistent across the two measures (weight regulation and portion size) scores will be averaged.

7.2.3. Other variables

BMI. Calculated as weight (kg) / Height (m²)

Aim guessing. Participants who identify the aim of the study as being to examine the influence of portion/meal size on food intake/appetite will be coded as being aware of the study aims. Responses will be independently coded by two researchers, with discrepancies in coding decisions resolved by a third researcher.

Manipulation awareness. Two binary variables: self-reported awareness (0: unaware, 1: aware) and observed awareness (0: wrong answer to ordering task, 1: right answer to the ordering task).

Liking, familiarity, and normality ratings. Scores range: 1 to 7.

7.3. Missing data

We do not anticipate missing data on energy intake due to participant non-attendance (if a participant misses a meal and it is not possible to reschedule for a later time that day, they will be required to begin that study day again). Every effort will be made to keep the number of missing data due to researchers' error to the lowest. The extent of the missing data will be reported. We plan to analyse complete cases only.

Missing data on other variables will not be allowed by the experimental procedure because the record for each participant will be checked after each study day and the participants will be asked to provide their answers again if case of any missing data.

7.4. Primary analyses

7.4.1. Confirmatory analyses

To be consistent with previous studies we ran investigating the effect of SEP on intended energy consumption (e.g [45]), the primary measure of SEP used in our primary analysis will be highest educational qualification (binary – lower vs higher).

A mixed ANOVA will be used to test the effect of portion size (categorical: larger, smaller; within-subject), SEP (categorical: lower (\leq A level), higher ($>$ A level), between-subjects), the interaction portion size*SEP on daily energy intake. If the interaction between portion size*SEP is significant the analysis will be stratified by SEP (\leq A level, $>$ A level) and two repeated-measures t-tests will be used to examine the effect of portion size (larger vs smaller) on daily energy intake in the two groups of participants separately. We will not correct for multiple comparisons as we specified a priori hypotheses.

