3. EXPERIMENTAL DESIGN

Participants will be randomised into a cross-over design with two study days corresponding to two conditions: larger portion size condition or smaller portion size condition. Each study day will last one day and be separated by a minimum 1-week and maximum 6-week washout period. The two study days will be scheduled for the same day each week. On both days, participants will be served all meals *ad libitum* in the lab (including breakfast and second helpings) and will be provided with snacks to consume outside of the lab – but only the size of the initial portion of the main meal provided for lunch and dinner will be manipulated. Energy intake from all meals and snacks will be recorded.

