5. METHODS

5.1. Test meals

The portion-manipulated test meals will consist of a pasta-based dish for lunch (3 cheese pasta), and a dish served with rice for dinner (chilli con carne), see Table 1 for more information about the dishes. The portion sizes are informed by pilot studies, including pilot studies conducted to assess the norm range, with portions in the larger portion size condition from the mid-higher end of the range, and portion sizes in the smaller portion size condition from the lower end of the norm range (see **Appendix A**).

Table 1. Portion sizes for each portion-manipulated dish in g and kcal

	Larger portion size (100%)			Smaller portion size (67%)		
	g	kcal	£	g	kcal	£
Lunch						
3 cheese pasta	563	816	2.46	375	544	1.64
Dinner						
Chili con carne & rice	437	509	0.90	291	339	0.60
Dinner including cheese and vegetables on the side (totals)	557	737	1.24	411	568	0.94

On each study day, all participants will receive the same *ad libitum* breakfast in the lab (initial serving providing 1437 kcal) and the same snack box for consumption away from the lab throughout the day (providing 906 kcal). At lunch, participants will have the opportunity to serve themselves more of the main dish. At dinner, participants will be served their main dish with a side of vegetables and they will also have the opportunity to request seconds of the main dish. After their dinner a dessert buffet with three options will be provided (providing 1528 kcal). Chilled water (500mL) will be served with each in-lab meal. The complete study menu can be found in SEP_portion_size MENU_UPDATED_TL.xlsx.

Participants will be requested 1/ not to consume any additional food apart from the items provided as part of the study, and 2/ drink only tea, coffee, and no calorie drinks (water) as they usually would.

Note for each self-service breakfast meal we will also vary the size of the dishware (smaller vs larger), the results of which will be reported in detail elsewhere. Given evidence to date (e.g. [47,48]), we expect this to have no impact on energy intake at breakfast, and this will be tested in analyses (see analysis plan). Manipulation of dishware size (smaller followed by larger dishware size

vs larger followed by smaller dishware size) will be fully counterbalanced with the order of portion size presentation (smaller followed by larger portions vs larger followed by smaller portions).

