RANDOMISATION	
 ▪ Participants will be randomly assigned to receive the larger portion sizes at the first experimental session and the smaller portion sizes at the second experimental session or vice versa. ▪ A randomisation sequence will be created using Random Allocation Software [35] with a 1:1 allocation stratified by highest educational qualification (Group 1: low ≤ A level, 18-25 years; Group 2: low ≤ A level, 26+ years, Group 3: ≥ degree, 18-25 years, Group 4: ≥ degree, 26+ years). ▪ The allocations will be placed inside envelopes for each group; the envelopes will be sequentially opened each time a participant from one group consent to take part in the study. ▪ Participants' two experimental sessions should take place on the same day of the week
STUDY DAY 1	
 ▪ Remind allowed food / drink, physical activity restriction and install the FitBit ▪ Sleep, mood, and hunger ratings ▪ Breakfast 30 minute session between 7 am and 10:30 am ▪ Snack box 
 ○ Provide the snack box after breakfast ▪ Lunch 30 minute session (between 12pm and 2pm) ▪ Dinner 30 minute session (between 5pm and 7pm – at least 4 hours after lunch) ▪ Organise the following steps: 
 ○ Remind the date of the next session (washout)
WASHOUT SESSION	
 ▪ Participants return FitBit device and snack box ▪ Check if any additional foods/drinks consumed ▪ Remind participants about date of next session (Study Day 2)

STUDY DAY 2	
 ▪ Remind allowed food / drink, physical activity restriction and install the FitBit ▪ Sleep, mood, and hunger ratings ▪ Breakfast 30 minute session between 7 am and 10:30 am ▪ Snack box 
 ○ Provide the snack box after breakfast ▪ Lunch 30 minute session (between 12pm and 2pm) ▪ Dinner 30 minute session (between 5pm and 7pm – at least 4 hours after lunch) ▪ Organise the following steps: 
 ○ Remind the date of the next session (final session)

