7.4.2. Sensitivity analyses

Sensitivity analyses will be conducted to examine whether the pattern of results from the main analyses differ after 1/ excluding participants guessing the aims of the study, 2/ excluding outliers on main outcome variables (identified as those with a value $>$ 3SD from condition mean) and influential cases (identified as those with a Cook's distance $>$ 1, indicating a multivariate outlier [37], 3/

substituting SEP measure (highest educational qualification, \leq A level, $>$ A level) with alternative measures of SEP (level of education – composite score, subjective socioeconomic status (1-10), and household income).

The main analyses will also be repeated controlling for any non-SEP based demographic variables (e.g. BMI, age) that significantly differ between the higher vs. lower SEP groups in order to examine if results remain consistent. To examine whether the order that portions are presented impacts the findings, the main analyses will be repeated with an additional 2-level between-subjects factor (portion size order: smaller, larger vs larger, smaller). Finally, the main analyses will be repeated with dishware size as an additional 2-level within-subjects factor (dishware size: smaller vs larger).

We will report whether sensitivity analyses result in deviations from the pattern of significance to the main analyses (i.e., any significant differences between conditions becoming not significant, and vice versa).

Note if $>30\%$ participants guess the study aim we will include aim guessing as a between-subjects factor in ANOVA rather than use listwise removal.

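### The primary ANOVA leaves out portion order, the factor that is randomised, so any day-1/day-2 shift in intake costs precision in both primary tests

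*Combined protocol and SAP*

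**What the plan says.** The confirmatory analysis (section 7.4.1) reads "A mixed ANOVA will be used to test the effect of portion size", with SEP between subjects and the portion size by SEP interaction. It has no order, day or breakfast term. A significant interaction leads to separate paired t-tests within each SEP group.

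The randomised factor is the order of the portions (section 6, Table 2): "Participants will be randomly assigned to receive the larger portion sizes at the first experimental session and the smaller portion sizes at the second" session, or the reverse. Allocation is 1:1 within four education-by-age strata.

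Order is used in section 7.4.2: "the main analyses will be repeated with an additional 2-level between-subjects factor", namely portion size order. Dishware gets similar treatment: "the main analyses will be repeated with dishware size as an additional 2-level within-subjects factor". Section 5.1 says that the dishware manipulation "will be fully counterbalanced with the order of portion size presentation".

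On breakfast, section 3 says that "only the size of the initial portion of the main meal provided for lunch and dinner will be manipulated". The ad libitum breakfast (initial serving 1437 kcal, section 5.1) thus precedes each day's manipulated meals. It is summed into the primary outcome (section 7.2.1), and no analysis adjusts for the amount eaten. The study days are "separated by a minimum 1-week and maximum 6-week washout period".

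**The concern.** Both primary tests rest on the variance of each participant's larger-minus-smaller difference in daily intake. If intake differs systematically between day 1 and day 2, for example through familiarity with the laboratory, the shift adds to that difference in one order group and subtracts from it in the other. A model without order counts this spread as noise. A model with order removes it at the price of one degree of freedom.

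The sensitivity analysis would show the order-adjusted result, but the less precise test would still govern the trial's conclusion. With 46 to 60 participants, precision that comes free from the design is worth taking.

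**Working it through.** **Inputs.** From section 7.6: f = 0.175, within-subject correlation 0.7, 85% power, N = 46, possibly 60. From section 7: two-sided alpha 0.05. Assumed, because the documents give no value: a day shift π of 0.1, 0.2 or 0.35 SD of daily intake.

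**The plan's own figure.** Let D be the larger-minus-smaller difference, in SD units of daily intake.
- Mean of D = 2f = 0.35. Variance of D = 2(1 − 0.7) = 0.6.
- Noncentrality λ = N × 0.35² / Var(D) = 46 × 0.1225 / 0.6 = 9.39.
- With 1 and 44 df, power is 85.0%, so N = 46 reproduces. At N = 60, λ = 12.25 and power is 93.1%.

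**Adding a day shift.** D = 0.35 + π × o + error, where o is +1 if the larger portion falls on day 2 and −1 if on day 1. With balanced orders the shift contributes π² to the variance that a model without order sees. The result depends on what the 0.7 represents, and section 7.6 does not say.

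*Reading 1: 0.7 is net of the day shift.* The planned ANOVA works with variance 0.6 + π²; the model with order works with 0.6.

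| π (SD) | Variance, order omitted | λ, N=46 | Power without order, N=46 | Power without order, N=60 |
|---|---|---|---|---|
| 0.1 | 0.61 | 9.24 | 84.4% | 92.7% |
| 0.2 | 0.64 | 8.80 | 82.7% | 91.5% |
| 0.35 | 0.7225 | 7.80 | 78.0% | 88.0% |

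With order, power is 85.0% and 93.1%. Simulation with order balanced within SEP groups gives slightly higher power for the planned test: 84.4, 83.1 and 79.8% at N=46, and 92.8, 92.0 and 90.0% at N=60.

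*Reading 2: 0.7 is a raw figure that already contains the shift.* By the plan's formula the ANOVA has 85.0%; the model with order works with variance 0.6 − π².

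| π (SD) | Variance, order included | λ, N=46 | Power with order, N=46 | Power with order, N=60 |
|---|---|---|---|---|
| 0.1 | 0.59 | 9.55 | 85.6% | 93.4% |
| 0.2 | 0.56 | 10.06 | 87.3% | 94.5% |
| 0.35 | 0.4775 | 11.80 | 91.9% | 97.1% |

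Here too, balanced orders would put the planned test somewhat above its formula value, so these gains are upper figures.

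**Cost if there is no shift.** With balanced orders, one df fewer (43 for 44) costs under 0.1 point. If order were simply randomised without balance, simulated power is 84.2% at N=46 and 92.6% at N=60, a loss of about 1 point at most.

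**Error rate.** With a 0.35 SD shift and balanced orders, the simulated type I error of the interaction test is 3.3% (N=46) and 3.1% (N=60) without order, and 5.3% and 5.1% with it. The planned test is conservative.

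**Interaction.** For a gap Δ in the portion size effect between equal SEP groups, λ = NΔ² / (4 Var(D)).
- The planned f = 0.175 corresponds to Δ = 0.70: 46 × 0.49 / 2.4 = 9.39, or 85% power.
- Δ = 0.35, a gap as large as the whole planned main effect: 46 × 0.1225 / 2.4 = 2.35, or 32%. At N=60, λ = 3.06, or 41%.
- With order included, in the most favourable case above (reading 2, π = 0.35): 46 × 0.1225 / (4 × 0.4775) = 2.95, or 39%.

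**Breakfast.** Only day-to-day variation matters here, because stable habits cancel in D. Let r be the assumed correlation between the breakfast difference and D. With SEP, order, dishware pairing and the breakfast difference in the model, no day shift, and 0.7 taken as raw, power at N=46 is 84.0% at r = 0, 85.4% at 0.2, 87.2% at 0.3 and 92.6% at 0.5. Break-even against 85.0% is r of about 0.17.

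**The case against.** The strongest reply is that nothing is wrong with the planned test. Allocation is 1:1 and stratified, a 2×2 mixed ANOVA is valid, order is already a planned sensitivity factor, and section 7.4.2 commits to reporting any change in significance. The gain rests on a day shift that nobody has measured. If the partial η² of 0.41 cited in section 7.6 held here, the standardised paired effect would be √(0.41/0.59) ≈ 0.83 and power for the main effect at N=46 would exceed 99.9%.

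Most of this stands, and it limits the point to efficiency. It does not remove it: the change moves a term that is already planned, costs almost nothing when there is no shift, and lets the more precise test carry the conclusion.

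A reader might infer three stronger things that the documents do not support.
- **That omitting order biases the portion size effect or inflates type I error.** That needs clearly unequal orders. At an assumed 28:18 split with a 0.3 SD shift, the estimate moves by 0.3 × 10/46 = 0.065 SD and simulated type I error is 6.9%. Stratified 1:1 allocation makes such a split unlikely, although no block size is stated and the analysis is of complete cases.
- **That the planned power is really below 85%.** This follows only if 0.7 is net of the shift.
- **That breakfast intake belongs in the primary model.** Its benefit needs an undocumented r above about 0.17, and participants who offset a larger breakfast later in the day would lower r. Day-2 breakfast also follows the day-1 condition, so the adjustment assumes no carry-over.

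**Conclusion.** The point holds as a modest precision improvement. The primary model omits the randomised factor, and any day shift then sits in the error term of both primary tests. For assumed shifts of 0.1 to 0.35 SD at N=46, including order is worth roughly 1 to 7 points of power for the portion size effect. The figure depends on the shift and on whether 0.7 is net or raw, neither of which the documents settle. With near-balanced orders there is no bias, and the planned tests err on the conservative side. The omission does not explain, and its repair does not cure, the low power for a 0.35 SD SEP gap. Breakfast adjustment is an option, not a correction.

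**What to change.** **Primary model.** Add portion order as a between-subjects factor, with its portion size by order term, which absorbs the day shift. Equivalently, regress each participant's larger-minus-smaller daily intake on SEP and order, both coded ±1: the intercept tests the portion size effect and the SEP coefficient tests the interaction. Specify no SEP by order term; a full factorial would break the exact equivalence and use a further df. Take the SEP-specific effects from this model (intercept plus or minus the SEP coefficient) in place of the separate t-tests. Keep the unadjusted 2×2 ANOVA as the sensitivity analysis. If the regression form is used, the SEP main effect comes from that ANOVA.

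**Optional, pre-specified sensitivity analysis.** Add the larger-day minus smaller-day breakfast difference, with dishware entered as a pairing, because two study days give each participant only two of the four portion-by-dishware cells. Leave the breakfast difference uncentred, so that zero means equal breakfasts: in a null simulation at N=46, centring at the sample mean raised type I error to 6.0% at r = 0.3 and 9.3% at r = 0.5, against 5.2% uncentred. State the no-carry-over assumption. If the day-1 condition changes day-2 breakfast by an amount that differs by C between orders, the adjusted and unadjusted effects differ by slope × C/2; an assumed slope of 0.7 and C of 60 kcal give 21 kcal.

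**Cost.** Only the SAP changes; every variable is already collected. The order term uses one df. The other sensitivity analyses that repeat the main analysis need matching wording, and section 7.5.1 should say whether the mediation models also include order.

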7.4.2. Sensitivity analyses

Sensitivity analyses will be conducted to examine whether the pattern of results from the main analyses differ after 1/ excluding participants guessing the aims of the study, 2/ excluding outliers on main outcome variables (identified as those with a value $>$ 3SD from condition mean) and influential cases (identified as those with a Cook's distance $>$ 1, indicating a multivariate outlier [37], 3/

substituting SEP measure (highest educational qualification, \leq A level, $>$ A level) with alternative measures of SEP (level of education – composite score, subjective socioeconomic status (1-10), and household income).

The main analyses will also be repeated controlling for any non-SEP based demographic variables (e.g. BMI, age) that significantly differ between the higher vs. lower SEP groups in order to examine if results remain consistent. To examine whether the order that portions are presented impacts the findings, the main analyses will be repeated with an additional 2-level between-subjects factor (portion size order: smaller, larger vs larger, smaller). Finally, the main analyses will be repeated with dishware size as an additional 2-level within-subjects factor (dishware size: smaller vs larger).

We will report whether sensitivity analyses result in deviations from the pattern of significance to the main analyses (i.e., any significant differences between conditions becoming not significant, and vice versa).

Note if $>30\%$ participants guess the study aim we will include aim guessing as a between-subjects factor in ANOVA rather than use listwise removal.

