4. PARTICIPANTS AND RECRUITMENT

4.1. Recruitment

Recruitment advertisements will be placed on social media (Facebook, Instagram, Twitter), online noticeboards (Gumtree, Call for Participants), and University of Liverpool (and other local universities') staff and students announcements and mailing lists. Flyers and posters will be distributed around the University of Liverpool campus, and if needed in local businesses and via letterbox drops in local residences with a particular focus on the most deprived areas based on the Index of Multiple Deprivation (IMD). Participants will be reimbursed for their time and expenses (£70 at the end of the study).

Recruitment will be stratified by highest educational qualification achieved or currently studying for as follows:

- 50% lower qualification levels

- No formal qualifications
- 1–3 GCSEs or equivalent
(*Level 1: first certificate; GCSE – grades 3, 2, 1 or grades D, E, F, G; level 1 award; level 1 certificate; level 1 diploma; level 1 ESOL; level 1 essential skills; level 1 functional skills; level 1 national vocational qualification (NVQ); music grades 1, 2 and 3*)
- 4+ GCSEs or equivalent
(*Level 2: CSE – grade 1; GCSE – grades 9, 8, 7, 6, 5, 4 or grades A*, A, B, C; intermediate apprenticeship; level 2 award; level 2 certificate; level 2 diploma; level 2 ESOL; level 2 essential skills; level 2 functional skills; level 2 national certificate; level 2 national diploma, level 2 NVQ; music grades 4 and 5; O level – grade A, B or C*)
- A level or equivalent
(*Level 3: A level; access to higher education diploma; advanced apprenticeship; applied general; AS level; international Baccalaureate diploma; level 3 award; level 3 certificate; level 3 diploma; level 3 ESOL; level 3 national certificate; level 3 national diploma; level 3 NVQ; music grades 6, 7 and 8; tech level*)
- 50% higher qualification levels
 - Certificate of higher education (CertHE) or equivalent
(*Level 4: certificate of higher education (CertHE); higher apprenticeship; higher national certificate (HNC); level 4 award; level 4 certificate; level 4 diploma; level 4 NVQ*)
 - Diploma of higher education (DipHE) or equivalent
(*Level 5: diploma of higher education (DipHE); foundation degree; higher national diploma (HND); level 5 award; level 5 certificate; level 5 diploma; level 5 NVQ*)
 - Bachelor or equivalent

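### The Cook's distance > 1 rule for influential cases is practically unreachable in the primary two-group model, and the 3 SD rule beside it covers only part of the gap

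*Combined protocol and SAP*

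**What the plan says.** Section 7.4.1 defines the main analysis: "A mixed ANOVA will be used to test the effect of portion size (categorical: larger, smaller; within-subject), SEP" and their interaction, with daily energy intake as outcome and no covariates. SEP enters in two groups: "the primary measure of SEP used in our primary analysis will be highest educational qualification (binary – lower vs higher". Section 4.1 sets the recruitment target at "50% lower qualification levels" and the same share of higher levels. Section 7.6 gives a minimum of 46 participants and a maximum of 60.

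Item 2 of the sensitivity analyses in section 7.4.2 has two exclusion rules. One acts on intake: "excluding outliers on main outcome variables (identified as those with a value $>$ 3SD from condition mean". The other acts on influence, and removes any case with a Cook's "distance $>$ 1, indicating a multivariate outlier". The section does not name the regression from which Cook's distance is taken and gives no other influence criterion. It undertakes to report whether the sensitivity analyses change the pattern of significance. Section 7.3 restricts the analysis to complete cases.

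**The concern.** Cook's distance combines the size of a residual with leverage. In a model containing only a balanced grouping factor, all participants have the same, low leverage, and a single residual can grow only so far relative to a residual variance that it inflates itself. A cut-off of 1 may then lie at or beyond the edge of what is possible.

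In a trial of 46 to 60 women, it is reasonable to ask whether one participant drives, or hides, the portion size by SEP interaction. If the influence rule cannot respond, a finding of no influential cases says nothing about that question. The matter then rests on the 3 SD rule, which looks at each day's intake, whereas the interaction is tested on the difference between days.

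**Working it through.** **Inputs.** From section 7.6: N = 46 to 60, f = 0.175, two-sided 5%, 85% power, within-subject correlation 0.7. From section 7.4.1: two portion levels, two SEP groups, no covariates. From section 4.1: a 50/50 split. From section 7.4.2: Cook's distance > 1 and the 3 SD rule.

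**The plan's own figure.** The noncentrality is f² × N × 2/(1 − 0.7) = 0.030625 × 46 × 2/0.3 = 9.39. Power for the interaction on (1, 44) degrees of freedom is 0.850, so N = 46 reproduces. The expected t is √9.39 = 3.06.

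**Ceiling with equal groups.** Cook's D = (r²/p) × h/(1 − h), where r is the internally studentised residual, p the number of parameters and h the leverage. Always r² ≤ N − p. For the PSE regressed on SEP, or for either day's intake, p = 2 and h = 2/N:

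- N = 46: (44/2) × (1/22) = 1
- N = 60: (58/2) × (1/29) = 1
- Long format at N = 46 (92 rows, four cell means): (88/4) × (1/22) = 1

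Adding subject fixed effects also gives 1. In general, equal leverages mean h = p/n, and ((n − p)/p) × (p/n)/(1 − p/n) = 1. Reaching 1 requires every other residual to be zero; exceeding it is impossible.

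**Numerical check.** With one participant shifted by 5, 10 or 100 SD, the median largest D is 0.36, 0.69 and 0.996 at N = 46, and 0.29, 0.64 and 0.994 at N = 60. In 200,000 Cauchy data sets at each N, none gave D > 1.

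**Ceiling with unequal groups.** For a participant in the smaller group, of size n₁, D ≤ ((N − 2)/2)/(n₁ − 1). D > 1 needs r² > 2(n₁ − 1), so that omitting her would remove more than 2(n₁ − 1)/(N − 2) of the residual sum of squares.

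| Split (N = 46) | Ceiling | Share needed | Externally studentised residual needed |
|---|---|---|---|
| 22/24 | 22/21 = 1.05 | 42/44 = 95% | 30.0 |
| 20/26 | 22/19 = 1.16 | 38/44 = 86% | 16.5 |

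At N = 60, splits of 29/31 and 26/34 give ceilings of 29/28 = 1.04 and 29/25 = 1.16.

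**What the 3 SD rule catches.** With correlation 0.7, the SD of the PSE is √(2 × 0.3) = 0.775 intake SD. A 5 SD shift in the PSE is therefore 3.87 intake SD, or 1.94 per day if split evenly over the two days. Simulation with normal intakes at N = 46 and 60 gave these catch rates:

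- 10 SD: about 91–100%
- 5 SD, all on one day: about 46–77%
- 5 SD, split over both days: about 9–23%

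**Consequence.** At N = 46 with the planned interaction present, a participant shifted by 5 SD against the effect, split over both days, moves t by about −1.2. The share of significant interactions falls from about 85% to 45%. The 45% is about the same when counted only over data sets in which the 3 SD rule passes her.

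**The case against.** Several objections have force.

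- **The 50/50 split is a target.** Analysed groups may differ in size, and the ceiling then rises above 1. A reader might infer that the rule can never fire; the documents do not support that. The table shows how little imbalance helps, so the supportable statement is practically unreachable.
- **No model is named for Cook's distance.** With continuous predictors, leverages are unequal and the ceiling no longer applies. An illustrative covariate with one 6 SD value gave a bound of about 24. Section 7.4.2 plans such models (age or BMI as covariates, subjective status), so the rule can work there. Item 2, however, is framed as a check on the main analyses, and those have no continuous predictor.
- **The 3 SD rule is in the same item.** A reader might infer that the whole sensitivity analysis is empty. It is not: that rule removes nearly all participants about 10 SD out on the PSE. The gap concerns moderate PSE outliers spread over both days.
- **An outlier need not create a false finding.** A reader might infer that one participant could manufacture the planned interaction. With the planned effect present, a 5 SD outlier favouring the hypothesis moves t by about 0, because it inflates the variance as well as the difference. The demonstrated risk is a masked interaction.
- **Reporting.** The plan does not say that an absence of influential cases will be presented as proof of robustness. It commits only to reporting changes in the pattern of significance.

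**Conclusion.** The influential-case rule is wrong as written for the primary model, with low to moderate severity. The ceiling of exactly 1 is algebra: it needs equal analysed groups and no continuous predictor, and does not depend on any variance or effect size. For modest imbalance the ceiling stays near 1, and only an absurdly extreme case would cross the cut-off.

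The practical size rests on assumptions: normal intakes, the plan's correlation of 0.7, the planned interaction, and one participant shifted by 5 SD. If her shift is spread over both days, the 3 SD rule misses her in roughly 77–91% of data sets and Cook's rule does not flag her. If she also opposes the effect, significance at N = 46 falls from about 85% to 45%. Nothing in the documents says that such a participant will occur.

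The primary estimand, estimate, test and sample size are untouched. What fails is one half of one sensitivity item.

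**What to change.** In section 7.4.2, keep the 3 SD rule. For the primary model, replace the Cook's distance rule with a leave-one-out analysis of the PSE regressed on SEP. With SEP coded −½ and +½, the intercept is the portion size effect and the slope the portion size by SEP interaction. Report the minimum and maximum of both estimates, with p-values, over all single omissions. This needs no cut-off.

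If an exclusion rule is wanted, apply an attainable one to the PSE model, such as the externally studentised residual at its Bonferroni limit. On N − 3 degrees of freedom that is |t| > 3.50 at N = 46 and 3.53 at N = 60. A Cook's cut-off of 4/N would go too far the other way: it flags at least one participant in about 97% of clean data sets at N = 46 and 99% at N = 60.

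If Cook's distance is kept for models with continuous predictors, name those models. The cost is a sentence or two in section 7.4.2 and a short loop in the analysis, with no extra data or participants.
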